3.3 Study Measures

AIM 1 Pilot study:

- **E-triage:** The e-triage will consist of 16 questions, modified from the validated NCI Pro-CTCAE™, which will be sent to patients via WaytoHealth®'s two-way texting system 96 hours prior to their scheduled immunotherapy infusion (see appendix B). Questions will pertain to common or emergent immune related adverse events as defined by the NCCN guidelines and two senior disease experts⁴²⁻⁴⁴. Patients will be prompted via text to measure the presence and severity of symptoms over the week prior. A final question will be included to capture any additional symptoms patients wish to disclose.
- **NCI Pro-CTCAE™:** A subset of patients may be asked to fill out a subset of the NCI PRO-CTCAE™, a set of validated questions for the collection of patient-reported outcomes to capture symptomatic adverse events in patients on cancer clinical trials, in order assess construct validity.
- **Definition of gold standard:** Patient reported toxicity captured by the text-based instrument will be compared to provider reported toxicity as documented in the EMR as the gold standard. To assess provider reported toxicity, standardized abstraction protocols will be developed by the PI and implemented by trained research staff.

AIM 2 Randomized control study:

- **Care time:** Care time will be defined as total time spent commuting to and receiving cancer care (including time spent obtaining labs). This will be captured using a combination of time-stamp information abstracted from AirFinder®, a real time patient located system deployed in the Perelman Cancer Clinics, and self-reported time for commuting and time spent obtaining local labs. Commute times will also be estimated using the patient's home address geocoded using ArcGIS software.
- **Emergency department and hospitalization rates:** Total number of emergency department visits and hospitalizations will be collected using data abstracted from the Penn electronic medical record during a 3 month follow-up window as well as through patient check-ins with study staff during routine infusion visits to account for care received outside the Penn system.

CONFIDENTIAL

- **Health related quality of life** : The Functional Assessment of Cancer Therapy-General (FACT-G) 27-item questionnaire will be used to measure four main domains of health related quality of life in cancer patients including physical, social, emotional and functional well-being⁴. The FACT-G takes approximately 5-10 minutes to complete. This will be completed at the time of enrollment and during each infusion visit.
- **Patient satisfaction**: The Patient Satisfaction Questionnaire-18 will be used to assess global satisfaction with medical care including six aspects of care: technical quality, interpersonal manner, communication, financial aspects of care, time spent with doctor, accessibility of care¹. The PSQ-18 takes approximately 3-4 minutes to complete. This will be completed at the time of enrollment and during each infusion visit.
- **Provider satisfaction**: The net-promoter score is a gauge of participant satisfaction taken by asking how likely they would be to recommend your service or program on a scale of 0-10^{2,3}. These will be completed at the time of study completion.

3.4 *Study Endpoints*

3.4.1 Primary Study Endpoint

AIM 1 Pilot: To assess the performance of the text-based e-triage system sensitivity and specificity with a gold standard will be determined.

AIM 2 Randomized control trial: The primary endpoint will be cumulative care time associated with cancer treatment, measured over a over three months or at least 3 infusion visits. We will define care time as total time spent commuting to and receiving care (including time spent obtaining labs).

3.4.2 Secondary Study Endpoints

AIM 2 Randomized control trial: Secondary endpoints will include total wait time (see attached study flowchart), total number of ED visits and/or hospitalizations, health related quality of life utilizing the FACT-G⁴, treatment satisfaction with the PSQ-18¹, and providers satisfaction using the net-promoter score^{2,3}.

4 Study Population and Duration of Participation

4.1 *Duration of Study Participation*

AIM 1 Pilot study: The duration of study participation will be 2 months from the date of enrollment.

AIM 2 Randomized control study: The duration of study participation will be the time it takes to complete 3 infusion visits, approximately 3 months..

4.2 *Total Number of Subjects and Sites*

Penn (Perelman Center for Advanced Medicine floors 2,3,4) will be the only site recruiting patients. For the pilot study we will enroll up to 100 patients over a 2-months. For the randomized control trial, to have 160 evaluable subjects, with an expected 10% drop out rate, we plan to enroll 176 patients.

4.3 *Inclusion Criteria*

AIM 1: Pilot participants:

- Over 18 years of age
- Access to mobile device with text messaging capabilities
- Receiving single agent PDL-1/PD-1 targeted immune checkpoint blockade for any solid malignancy
- Treating oncologist is at Penn's Abramson Cancer Center

AIM 2: Randomized control trial participants:

- Over 18 years of age

CONFIDENTIAL

- Receiving single agent PDL-1/PD-1 targeted immune checkpoint blockade for any solid malignancy
- Access to and ability to use a mobile phone with texting capabilities

4.4 Exclusion Criteria

- Non-English speaking
- Unable to perform informed consent

4.5 Subject Recruitment

A weekly screening list of potentially eligible subjects scheduled to received PD-L1/PD-1 pathway inhibitors at one of the Perelman infusion suites will be generated using EPIC. Trained research staff will then screen for eligible patients using strict inclusion and exclusion criteria (see 4.3) and contact treating physicians via email to request for permission to approach the patient at the time of their first immunotherapy infusion. Trained members of the research team will then approach the patient in-person during their infusion visit to assess interest and complete informed consent. If patients consent, they will be enrolled onto the study, but not randomized until the patients respond to an additional screening question sent via text 5 days following consent to ensure patient's engagement with the texting platform. Our recruitment strategy will be tailored as necessary under the advisement of [name], the Chair of Diversity and Inclusion, to minimize barriers to accrual for underrepresented groups.

4.6 Vulnerable Populations:

Children, pregnant women, fetuses, neonates, or prisoners are not included in this research study.

5 Study Procedures

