10.4	INFORMED CONSENT PROCESS / HIPAA AUTHORIZATION	18
10.4.1	Alterations to Typical Consent Process	18
11	STUDY FINANCES	19
11.1	FUNDING SOURCE	19
11.2	CONFLICT OF INTEREST	19
12	PUBLICATION PLAN	19
13	REFERENCES	19

Study Summary

Title	Text-based intervention to minimize the time burden of routine cancer care
Short Title	TIME
IRB Number	
Protocol Number	UPCC 16921
Methodology	This is a randomized control trial of a text-based mobile intervention to triage patients prior to treatment with single agent checkpoint blockade. Our hypothesis is that the use of a text-based e-triage prior to treatment will lower total healthcare time relative to standard office visit.
Study Duration	1 year
Study Center(s)	Single center 
• Perelman Center for Advanced Medicine at the Hospital of the University of Pennsylvania
Objectives	
Primary:
 
• To measure and refine the performance of a text-based instrument to assess patient-reported immunotherapy toxicity by determining sensitivity and specificity against the gold standard-in person provider assessment as documented in the electronic medical record (EMR).• To compare total care times, defined as time spent commuting to, waiting for, and receiving care, associated with a text-based e-triage system versus standard office visit among patients with advanced cancer receiving immunotherapy over a three-month period. 
Secondary:
 
• To determine whether a text-based e-triage affects healthcare quality of life as well as treatment and provider satisfaction.• To determine whether a text-based e-triage affects total number of emergency department visits and hospitalizations.
Number of Subjects	Up to 100 patients will be enrolled for the pilot study. 176 will be enrolled for the randomized control trial.
Main Inclusion and Exclusion Criteria	
Inclusion criteria
 
• Age 18 or older and able to give informed consent• English speaking• Receiving single-agent PDL-1/PD-1 checkpoint blockade• Diagnosed with a solid tumor malignancy• Access and ability to use a mobile phone with text-messaging capabilities•

CONFIDENTIAL

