6.1 Sample Size and Power Determination

AIM 1 Pilot study: This protocol describes a cross-sectional study designed to investigate the operating characteristics of a text-based e-triage to capture patients experiencing immune-related adverse events against the gold standard of documented toxicity assessments in the EMR. Due to the granular nature of our e-triage questionnaire we believe a sensitivity of 95-100% is very reasonable to anticipate.

Results from the interim analysis including 48 patients are shown in Table 1. Median age was 68.5 (IQR 58-72), 58% were female, 88% white, and most patients either had thoracic (25%), genitourinary (27%), head/neck (15%), or skin (15%) cancers. 53.2% of patients had at least 1 toxicity related adverse event documented in the EMR. Sensitivity to identify at least one toxicity related adverse event was 100% (95% CI 0.863-1.00) aligning with our primary endpoint. Despite being at our target sensitivity we identified two underperforming questions (pain and rash) and therefore optimized the instrument creating a version 2 (see appendix). Assuming the sensitivity and prevalence are same as those in the preliminary data, a sample of 47 patients will produce adequate precision for the estimate for sensitivity, with the half width of the 95% confidence interval no larger than 7%.

AIM 2 Randomized control trial: We plan to enroll 176 patients and expect to have 160 patients left assuming a 10% drop out rate (e.g., due to disease progression and need to change therapy). Based on the preliminary data recently published by this group measuring total care time of patients treated at the Penn Abramson Cancer Center⁸, we expect the total care time in the control group to have a mean of 130 hours with a SD of 118. A sample size of 80 per group will provide 79% power to detect a 40% reduction in the total care time (130 vs. 78) assuming a type I error rate of 0.05.

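### The target of 176 yields about 158 evaluable patients rather than 160, and the plan does not say whether 176 counts patients who consent or patients who are randomized

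*Protocol*

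**What the plan says.** The study summary at the front of the protocol says that "176 will be enrolled for the randomized control trial". Protocol section 4.2 says "to have 160 evaluable subjects, with an expected 10% drop out rate, we plan to enroll 176 patients". Section 6.1, repeated in SAP 1.1, says "expect to have 160 patients left assuming a 10% drop out rate (e.g., due to disease progression and need to change therapy"), so the drop-out causes are given as examples.

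The power statement in section 6.1 and SAP 1.1 rests on the resulting 160. For the control arm, "we expect the total care time in the control group to have a mean of 130 hours with a SD of 118". The claim for the sample size is "80 per group will provide 79% power to detect a 40% reduction in the total care time (130 vs. 78) assuming a type I"; the significance level used there is 0.05.

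Section 4.5 describes how patients enter the trial. After consent, "they will be enrolled onto the study, but not randomized until the patients respond to an additional screening question sent via text 5 days" later. The purpose of the question is stated too: it is sent "following consent to ensure patient's engagement with the texting platform".

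Neither document gives a number to be randomized, an expected rate of non-response to this text, or a rule for replacing those who do not answer.

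**The concern.** Two things do not fit together.

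First, the drop-out allowance was applied in the wrong direction. To keep 160 after losing 10%, the starting number must be divided by 0.9. Adding 10% to 160 gives 176, and 10% of 176 is more than 16.

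Second, the sample size is expressed in enrolled patients, and section 4.5 uses that word for a step before randomization. A study team applying section 4.5 literally would stop accrual at 176 consents. Anyone who had not answered the text would be inside the 176 but in neither arm.

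At stake are the evaluable number and the power computed from it. Planned power is already just under 80%, so there is little reserve for a loss that was not counted. The validity of the comparison is not at stake: non-response before randomization affects numbers and generalizability but does not bias the comparison between arms.

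**Working it through.** **Inputs from the documents.** Control mean 130 h, SD 118 h, intervention mean 78 h, 80 per group, type I error 0.05, stated power 79% (Protocol 6.1, SAP 1.1). Two-sample t test (Protocol 6.2 and 6.3.2, SAP 1.2 and 1.3.2). Allocation 1:1 (Protocol 3.2). Enrolment 176, drop-out 10%, evaluable 160 (Protocol 4.2 and 6.1, SAP 1.1).

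**Inputs assumed.** The SD of 118 h is taken for both arms. The test is taken as two-sided, which the plan does not state. The run-in non-response rate f is not in the documents and is varied below.

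**Step 1: reproduce the stated power.** The difference is 130 − 78 = 52 h. With n per arm, the noncentrality parameter is 52 / (118 x √(2/n)). At n = 80 this is 52 / 18.66 = 2.79, and the noncentral t distribution gives 79.1% power, which matches the stated 79%. A one-sided test would give 87.3%, so the two-sided reading is the one that fits. The same method gives 67.9%, 79.1%, 87.6% and 93.4% for the four rows of Table 2, against 68%, 79%, 88% and 93% printed. The power calculation itself is sound.

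**Step 2: reproduce the enrolment figure.**
- 160 x 1.1 = 176, which is the plan's number.
- 160 / 0.9 = 177.8, so 178 are needed to keep 160 after 10% loss.
- 176 x 0.9 = 158.4, or 79.2 per arm.
- The loss that would take 176 to 160 is 1 − 160/176 = 9.1%, not 10%.

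At 79.2 per arm the noncentrality parameter is 2.77 and power is 78.7%. The slip costs 1.6 evaluable patients and 0.4 percentage points.

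**Step 3: add the run-in, if 176 counts consented patients.** Randomized = 176 x (1 − f). Evaluable = 176 x (1 − f) x 0.9. Number to consent in order to keep 160 = 160 / (0.9 x (1 − f)), rounded up.

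| Assumed non-response f | Randomized | Evaluable | Power | Consents needed for 160 |
|---|---|---|---|---|
| 0% | 176.0 | 158.4 | 78.7% | 178 |
| 2% | 172.5 | 155.2 | 77.9% | 182 |
| 5% | 167.2 | 150.5 | 76.6% | 188 |
| 10% | 158.4 | 142.6 | 74.3% | 198 |
| 20% | 140.8 | 126.7 | 69.2% | 223 |

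The 0% row also applies if 176 is the number randomized, or if non-responders are replaced. The other rows take the 10% drop-out as a separate loss after randomization, which the plan does not confirm.

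**The case against.** The strongest reply is that 176 is naturally read as the trial sample. The summary ties it to the randomized trial, and section 6.1 and SAP 1.1 go straight from 176 to 160 to 80 per group. Section 4.5 calls the text an additional screening question, so those who do not answer could be treated as screening failures outside the 176. On that reading the run-in costs nothing and only the two-patient slip remains. This is a fair reading and cannot be ruled out. However, section 4.5 also says that these patients are already enrolled, and that is the unit in which the target is written, so the text supports both readings.

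Three stronger inferences are tempting, and the documents do not support them.
- A reader might infer that the run-in will certainly remove patients. Section 4.5 makes randomization wait for a reply, but it gives no deadline, no exclusion rule and no rate. Some loss is plausible, not stated.
- A reader might infer that the 10% covers only losses on treatment. Progression and change of therapy are introduced as examples, and section 4.2 gives the 10% with no cause. Run-in loss is not named, but it is not excluded either.
- A reader might infer that power is really near 70%. That needs both the consented reading and an assumed loss of about 20%, for which the plan offers no basis.

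The protocol also refers to a study flowchart and Appendix A, which are not in the text available here and may state the randomized number.

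**Conclusion.** The point holds, with modest certain consequences. On either reading of 176, a 10% loss leaves about 158 evaluable patients rather than 160, and power of 78.7% rather than 79.1%. Both figures round to 79%, so this part alone changes no conclusion about the design.

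The unit of the target is a real ambiguity, because it decides whether accrual stops at 176 consents or at 176 randomizations. Any further shortfall is conditional: it arises only if 176 counts consented patients, some do not answer, they are not replaced, and the 10% does not already include them. Under those conditions, assumed non-response of 5% to 10% would mean about 150 to 143 evaluable and power of 76.6% to 74.3%. The documents do not establish that any such loss will occur.

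**What to change.** In Protocol 4.2, Protocol 6.1 and SAP 1.1, state the target as patients randomized, and align the study summary with it. With 176 randomized, give the expected evaluable number as about 158 and the power as 78.7%. If 160 evaluable is to be kept, the number randomized is 178.

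If 176 is meant as the consented total, say so, state the assumed run-in loss and whether it is part of the 10%, and restate the expected randomized number, evaluable number and power. The size needed for 160 is then 160 / (0.9 x (1 − f)) when the two losses are separate. It would also help to say whether patients who do not answer the text are replaced.

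The cost is a few sentences and a slightly less favourable stated figure, or two more randomized patients if 160 is kept and 176 already means randomized. If 176 is the consented total and 160 is kept, the extra consents depend on the assumed loss. The design itself does not change.

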5.1 Screening

Patients will be offered the option to complete the initial educational visit either in-person or over a video-communication platform. At this visit patients will be enrolled onto the WaytoHealth© text messaging system and given instruction about the interphase. Trial protocol will be discussed in detail and patients will be provided with educational materials and study contact information. For patients on the randomized control trial baseline questionnaires (FACT-G and PSQ-18) will be completed.

5.2 Study timeline

5.2.1 Pilot

During the pilot, consented patients will be enrolled onto the Waytohealth© texting system and sent the text-based e-triage 4 days prior to their infusion. They will otherwise participate per their usual oncology care, which includes an in-person office visit. Following this visit, trained research staff will abstract relevant clinical information related to treatment toxicity as documented in the progress note from the electronic medical record.

5.2.2 Randomized control trial

For patients in the intervention arm, symptoms (using the text-based e-triage) and laboratory results (see appendix B) will be assessed 96 hours prior to the intended infusion date. A standardized algorithm to assess each laboratory value and clinical question will be used to triage patients. Those with normal laboratory tests and no flagged symptoms will proceed to their infusion without an office visit, those with either abnormal laboratory tests or any flagged symptoms will proceed to an in-person provider evaluation prior to their infusion (see appendix A). Providers and patients will be offered the option to override the system and request in-person evaluation. Patients in the control group will be assessed with standard in-person assessment. Patient time will be collected using an in-house real time tracking system via Bluetooth technology. There will be no additional visits required outside of those necessary for routine cancer care.

CONFIDENTIAL

Patients will be monitored for effects on health-related quality of life and treatment satisfaction at the time of consent and during their infusion for each cycle for a total of 3 cycles of therapy. Data will be collected during this time given that majority of immune mediated toxicity occurs prior to this timepoint^{44,46,47}.

5.2.3 End of Study Visit

The last visit will be during their final infusion during the follow-up window, at which time they will complete the FACT-G and PSQ-18 questionnaires as well as the opportunity to write an open-ended response regarding their experience with their program. At the same time, their physician will be asked to answer how likely they would be to recommend this program to a colleague on a scale of 1-10 through either email or EPIC inbox message according to physician preference.

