3.2 Allocation to Interventional Group

Patients will be randomized 1:1 to either the intervention (e-triage) or control (standard of care) arms using a randomization sequence created using the WaytoHealth® platform.

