Secondary endpoints include: total wait time measured, total number of hospitalization/emergency department encounters, patient satisfaction [The Patient Satisfaction Questionnaire Short Form (PSQ-18)]¹, provider satisfaction (Net-Promoter Score)^{2,3}, and health related quality of life [Functional Assessment of Cancer Therapy-General (FACT-G)⁴]. Total wait time and number of hospitalizations will be compared between groups using Wilcoxon rank sum test. The rest of the secondary endpoints will be measured at multiple time points and longitudinal linear mixed-effects model will be used to compare the group difference over time. Additional secondary analyses exploring changes in visit time across the duration of follow-up will also be performed.

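### Provider satisfaction is rated once, on an item with no control-arm version, yet the plan compares it between arms with a longitudinal model

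*Protocol*

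**What the plan says.** The Study Summary makes it a secondary objective to find out whether e-triage affects provider satisfaction. Protocol section 3.4.2 lists the endpoint as "providers satisfaction using the net-promoter score".

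Two sections describe the measurement. Section 3.3 defines the item as "asking how likely they would be to recommend your service or program on a scale of 0-10" and says of its timing: "These will be completed at the time of study completion". Section 5.2.3 attaches it to the visit that closes the patient's participation, for which it states: "The last visit will be during their final infusion during the follow-up window, at which time they will complete the FACT-G and PSQ-18 questionnaires". The provider rating belongs to that same occasion and is described there in these words: "their physician will be asked to answer how likely they would be to recommend this program to a colleague on a scale of 1-10".

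Protocol section 6.2, the Study Summary and SAP section 1.2 assign the Wilcoxon rank sum test to wait time and hospitalizations. They treat all other secondary endpoints, provider satisfaction included, as repeatedly measured, and state that a "longitudinal linear mixed-effects model will be used to compare the group difference over time".

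On the arms, section 3.2 says "Patients will be randomized 1:1 to either the intervention (e-triage) or control (standard of care) arms", and section 5.2.2 says "Patients in the control group will be assessed with standard in-person assessment". Neither document allocates or stratifies by physician.

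**The concern.** The arm label belongs to the patient, while the rating belongs to the physician and concerns a program. For the contrast to answer the objective, the question must mean something in both arms and the answer must be able to differ with the patient's arm. The documents secure neither. They also assign a model for repeated measurements to a score taken once.

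What is at stake is the reading of a null result. A difference near zero could be reported as showing that e-triage leaves provider satisfaction unchanged, when the item could have given that result whether physicians liked e-triage or not. The effect is confined to one secondary endpoint.

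**Working it through.** The plan states no power or precision figure for this endpoint; the Aim 2 power figures in section 6.1 and Table 2 concern total care time only. There is therefore no figure to reproduce, and the check is mainly a comparison of texts.

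**Step 1. Timing against model.** Sections 3.3 and 5.2.3 give one rating per patient, at the end. Section 6.2 and SAP section 1.2 need ratings at several time points. With one score per patient there is no change over time to estimate, so a group difference over time is undefined. A physician with several trial patients may give several ratings, but these are repeats within physician, and neither document says how they are handled.

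**Step 2. Who is asked.** Section 5.2.3 names no arm, so there are two cases.

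- *Physicians of control patients are asked.* Let a physician hold one view *v* of e-triage and have patients in both arms. The mean score is *v* under the intervention label and *v* under the control label. That physician contributes *v* − *v* = 0 to the arm difference for any *v*, and more patients do not change this.
- *They are not asked.* The control arm has no scores, so the planned comparison cannot be made.

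**Step 3. How common shared physicians would be.** Inputs: patient-level 1:1 allocation (section 3.2), taken as independent between patients, and *m* trial patients per physician. The documents do not give *m*, so a range is assumed. The probability that a physician has patients in both arms is 1 − 2 × 0.5^*m*:

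| *m* (assumed) | Calculation | Probability |
|---|---|---|
| 2 | 1 − 2 × 0.25 | 50% |
| 3 | 1 − 2 × 0.125 | 75% |
| 5 | 1 − 2 × 0.03125 | 93.8% |
| 8 | 1 − 2 × 0.00390625 | 99.2% |
| 10 | 1 − 2 × 0.0009765625 | 99.8% |

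On this assumption, most physicians with three or more trial patients would rate under both labels.

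**Step 4. Scale.** The 0-10 version has 11 points and midpoint 5.0; the 1-10 version has 10 points and midpoint 5.5. The linear map from the first to the second is *y* = 1 + 0.9*x*, so 0 becomes 1, 5 becomes 5.5 and 10 stays 10, a shift of 0 to 1 point. If one scale is used in both arms, a true difference *d* becomes 0.9*d* and a zero difference stays zero. The conflict affects which scores can be recorded; it does not bias the arm contrast by itself.

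**The case against.** The strongest reply is that no sentence says physicians of control patients rate e-triage. Two other readings are open. The item may go only to physicians of e-triage patients, as a measure of acceptability. Or it may concern whichever pathway the patient was assigned: section 3.3 speaks of a service or program, and section 5.2.3 has all patients comment on their experience of their program. On that second reading a control physician rates usual care and the contrast has meaning.

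This stands in part. That control physicians are asked is an inference from an arm-neutral visit description and a planned group comparison. But the first reading leaves no control data, and the second has no control-arm wording behind it, so physicians could be answering about different things. Neither clearly rescues the comparison.

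It is also fair that the zero in step 2 is conditional. The rating is requested patient by patient and could vary with that patient's course. Physicians whose trial patients all fall in one arm are outside the argument, and the number of patients per physician is unknown. A reader might infer that the expected arm difference is exactly zero whatever the merit of e-triage; the documents support only a tendency toward zero under the stated conditions.

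Finally, the endpoint is one of several secondary ones, and section 2.1 describes this work as exploratory. That limits the consequence but does not make the analysis fit the data.

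**Conclusion.** The point holds as a mismatch between item, timing and analysis. A single end-of-study rating cannot support the longitudinal model assigned to it. The between-arm comparison also cannot reliably show whether e-triage affects provider satisfaction: it tends toward zero if control physicians are asked about e-triage, and has no control data if they are not. A null result should not be read as no effect.

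The tendency toward zero rests on two assumptions: physicians have patients in both arms, and each holds one view of e-triage. The first has probability 50% to 99.8% for an assumed 2 to 10 trial patients per physician under independent allocation.

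Two stronger inferences are not supported. The ratings are not worthless, since scores from physicians of e-triage patients still describe acceptability. And the 0-10 versus 1-10 conflict is not a reason the comparison fails; it is a separate inconsistency to reconcile.

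The matter is minor in weight. The primary analysis is untouched.

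**What to change.** Remove provider satisfaction from the longitudinal between-arm model in protocol section 6.2, the Study Summary and SAP section 1.2. Ask the recommendation item once, at study end, of each participating physician who had e-triage patients. Report it descriptively with a confidence interval, as acceptability, and use the 0-10 scale in both section 3.3 and section 5.2.3. The cost is a dropped between-arm test and a possibly small sample of physicians, whose number the documents do not give. The Study Summary objective should then speak of acceptability to providers, not of an effect on their satisfaction.

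If a between-arm comparison is wanted, use an item about that patient's pre-infusion assessment, worded identically in both arms. Analyse it at the single time point with clustering by physician. The cost is larger: this replaces the net-promoter item and changes the endpoint text in both documents.
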